I will use only the informed consent form approved by Aldeyra Therapeutics, Inc. and by my IRB/REB/IEC and will fulfill all responsibilities for submitting pertinent information to the IRB/REB/IEC responsible for this clinical trial.

By my signature below, I attest that I have read, understand, and agree to abide by all the conditions, instructions, and restrictions contained in Protocol Number ADX-2191-RP-001, and will conduct the trial in accordance with the International Council for Harmonisation (ICH) guidelines on Good Clinical Practice (GCP) and applicable regulatory requirements.

Site Name

Site Address

[figure not shown]
Investigator's Printed Name

Investigator's Signature

Date

SUMMARY OF CHANGES

SYNOPSIS

Name of Sponsor: Aldeyra Therapeutics Inc.		Investigational Product: ADX-2191 (0.8% intravitreal methotrexate)
Title of Protocol: An open-label, phase II study of ADX-2191 in subjects with retinitis pigmentosa		
Protocol Number: ADX-2191-RP-001	Phase: Phase II	Indication for Use: Treatment of retinal dystrophy in patients with confirmed rhodopsin mutation
Subject Population: Adult subjects with retinitis pigmentosa and confirmed rhodopsin gene mutation (including P23H)		
Number of Subjects: Approximately 8 (eight) evaluable adult patients		
Number of Centers: Up to three investigational sites in the United States		
Duration of Subject Participation: 16 weeks		
Investigational Product: ADX-2191 (0.8% intravitreal methotrexate) 400mcg in 0.05ml		

Overall Design: In this open-label Phase II clinical trial, 8 (eight) subjects with retinitis pigmentosa due to rhodopsin mutations (including P23H) will be identified and treated with serial intravitreal injections of ADX-2191 in the worse seeing eye. Ocular structure and function will be evaluated.
 
Retinitis pigmentosa (RP) is an inherited retinal disease that leads to a progressive degeneration of photoreceptors. Mutations within the rhodopsin gene account for approximately 25% of autosomal dominantly inherited RP cases. The mutation P23H (Substitution of Proline to Histidine at Codon 23 of the rhodopsin protein) is the most common mutation in the rhodopsin protein gene. The P23H mutation is associated with misfolded rhodopsin, which causes endoplasmic reticulum overload, activates the unfolded protein response and triggers apoptosis. Intravitreal methotrexate has been demonstrated in pre-clinical models of retinitis pigmentosa to promote clearance of misfolded rhodopsin without an effect on wild type rhodopsin protein and improves electroretinogram (ERG) responses in P23H mutant rodents. (Liu et al. (2020). Pharmacological clearance of misfolded rhodopsin for the treatment of RHO-associated retinitis pigmentosa. The FASEB Journal, 34(8), 10146–10167.)
 
ADX-2191 is an intravitreal formulation of the active drug substance commonly known as methotrexate. The drug substance is formulated at a concentration of 400 µg/0.05 ml in a sterile, aqueous buffered solution designed for intravitreal delivery. The drug product is supplied in single-dose, 2 mL glass vials with a 0.5 mL fill volume.
 
In this open label study, the first four subjects (Cohort A) will be treated with monthly intravitreal injections of ADX-2191 for a total of three injections; the last four subjects (Cohort B) will be treated with twice monthly intravitreal injections of ADX-2191 for a total of six injections. All subjects will be followed for a total of 16 weeks following dosing.
 
Clinical trial procedures to be conducted are outlined in the Schedule of Assessments (Table 1).
		
Study Objective: To evaluate the safety and tolerability of ADX-2191 in patients with retinitis pigmentosa due to confirmed rhodopsin mutations, including P23H.		
Primary endpoint: The primary endpoints of this study are safety and tolerability.		

Secondary endpoint: The secondary endpoints include:

- 1) Best Corrected Visual Acuity (BCVA): Change in BCVA will be assessed using a normally illuminated ETDRS (Early Treatment Diabetic Retinopathy) chart.
- 2) Low-luminance visual acuity (LLVA): Change in Low-luminance visual acuity (LLVA) and the low luminance deficit (LLD) will be assessed. The LLD is defined as the difference between the BCVA and LLVA. LLVA will be assessed using a 2.0 log unit neutral density filter while reading a normally illuminated ETDRS (Early Treatment Diabetic Retinopathy) chart.
- 3) Macular Integrity Assessment (MAIA) Microperimetry: Central retinal sensitivity will be assessed using MAIA microperimetry using a standard 10-2 test grid with a Goldman size III stimulus of various intensities presented on a mesopic background (4 apostilbs).
- 4) Full field Electroretinography (ffERG): Change in dark-adapted flash ($0.01 \text{ cd} \cdot \text{s} \cdot \text{m}^{-2}$) b-wave amplitudes will be analyzed. Testing will be performed using a standard International Society for Clinical Electrophysiology of Vision (ISCEV) protocol.
- 5) Dark-Adapted Chromatic Perimetry: Change in dark adapted retinal sensitivity (dB) to the blue and red stimuli on the Medmont Dark-Adapted Chromatic (DAC) perimeter will be assessed.
- 6) OCT: Change in Central Subfield Foveal Thickness (CSFT) and Change in Ellipsoid Zone (EZ) area/width will be assessed using a spectral domain optical coherence tomograph (SD-OCT) volume scan using the Heidelberg Spectralis.

Safety: The safety and tolerability of ADX-2191 in subjects with retinitis pigmentosa due to confirmed rhodopsin mutations, including P23H, will be evaluated. Adverse Event data from Screening Visit A (Visit 1) until final study visit Visit 10 will be listed (by subject) and tabulated. Any serious adverse events will be described in subject narratives. In addition, any unanticipated adverse events will be separately tabulated. A urine pregnancy test will be performed at screening for women of childbearing age.

Study Population:

Inclusion Criteria - Preoperative

- 1) Up to 8 adult patients age 18 or older of any gender
- 2) Diagnosis of retinitis pigmentosa due to rhodopsin gene mutation, including P23H, confirmed previously by a CLIA or an investigational/academic lab
- 3) Impairment on VF in the opinion of the Investigator, as determined by perimetry
- 4) Willing to participate in the study as evidenced by signing of an informed consent document
- 5) Subjects of childbearing potential, both male and female, must agree to use two forms of birth control for the duration of the clinical trial. Males should continue to use the two forms of birth control for a minimum of three months after last injection (30 days after completion of Visit 9/Week 16). Females of childbearing potential must use the two forms of birth control for a minimum of 30 days following their last injection.
- 6) For females of child-bearing potential, subjects must have a negative pregnancy test at Screening and not lactating

Exclusion Criteria – Preoperative

- 1) Known allergy or hypersensitivity to methotrexate
- 2) BCVA worse than LogMAR BCVA 1.0 (Snellen equivalent 20/200) in the worse seeing eye
- 3) History of severe dry eye, corneal herpetic disease, LASIK, penetrating keratoplasty, or other significant corneal disease

- 4) Inability or unwillingness to use artificial tears during the study period
- 5) Pre-existing eye conditions or complicating systemic diseases that could interfere with the interpretation of the study or create inconsistent follow up. Examples may include severe cardiovascular disease, malignancy, profound amblyopia, diabetes or sickle cell disease if manifestation of advanced retinopathy is present, or subjects with immunodeficiency
- 6) Planned eye surgery during the study period
- 7) Participation in any clinical study of an investigational product within 90 days prior to enrollment and throughout enrollment period
- 8) Have previously received Methotrexate intravitreally or systemically within 3 months of Screening 1 visit
- 9) Patients who may need to use Methotrexate for another medical condition during the study period
- 10) Any history of systemic or ophthalmic condition or circumstances which, in the opinion of the Investigator, could compromise the subject's ability to comply with the protocol or that could compromise the subject's safety or the interpretation of the clinical trial results

Statistical Methods: Subject baseline characteristics, including demographics, concomitant diseases and medications, will be listed and tabulated. The intent to treat population is defined in the inclusion/exclusion criteria and is all subjects who have had ADX-2191 administered. No formal interim analysis is planned. Prior to database lock, the Sponsor will finalize a statistical analysis plan (SAP) detailing all planned analyses.

Table 1: Schedule of Events and Assessments

Assessment	Visit 1 (V1)	Visit 2 (V2)	Visit 3 (V3)	Visit 4 (V4)	Visit 5 (V5)	Visit 6 (V6)	Visit 7 (V7)	Visit 8 (V8)	Visit 9 (V9)	Visit 10 (V10)
	Screening Visit A	Screening Visit B Week 0	Day 4 ¹	Week 2 ²	Week 4 ²	Week 6 ³	Week 8 ³	Week 10 ³	Week 12 ³	Week 16 ³
Informed consent	X									
Eligibility criteria	X									
Demography, medical and ocular history	X									
Best Corrected Visual Acuity	X ⁴	X ^{4,6}	X ⁴		X ⁴		X ⁴		X ⁴	X ⁴
Low Luminance Visual Acuity	X ⁴	X ^{4,6}	X ⁴		X ⁴		X ⁴		X ⁴	X ⁴
Full ophthalmic exam, including intraocular pressure, slit lamp, and dilated funduscopy	X ⁴		X ⁴		X ⁴		X ⁴		X ⁴	X ⁴
Wide-field Color Fundus Photography and Autofluorescence	X ⁴								X ⁴	X ⁴
Macular SD-OCT (Spectral Domain Optical Coherence Tomography)	X ⁴				X ⁷		X ⁷		X ⁴	X ⁴
Dark-Adapted Chromatic (DAC) Perimetry	X ⁷	X ^{6,7}	X ⁷		X ⁷		X ⁷		X ⁷	X ⁷
Macular Integrity Assessment (MAIA) Microperimetry	X ⁷	X ^{6,7}	X ⁷		X ⁷		X ⁷		X ⁷	X ⁷
Full field electroretinography	X ⁴								X ⁴	
Cohort A (Monthly ADX-2191 injection)										
Corneal Slit Lamp Safety Exam		X ⁷								
Urine Pregnancy Test		X			X		X			
Intravitreal injection of ADX-2191		X ^{5,7}			X ^{5,7}		X ^{5,7}			
Concomitant medications	X	X	X		X		X		X	X
Adverse events	X	X	X		X		X		X	X
Cohort B (Bimonthly ADX-2191 injection)										
Corneal Slit Lamp Safety Exam		X ⁷		X ⁷		X ⁷		X ⁷		
Urine Pregnancy Test		X		X	X	X	X	X		
Intravitreal injection of ADX-2191		X ^{5,7}		X ^{5,7}	X ^{5,7}	X ^{5,7}	X ^{5,7}	X ^{5,7}		
Concomitant medications	X	X	X	X	X	X	X	X	X	X
Adverse events	X	X	X	X	X	X	X	X	X	X

¹: Visit window +/- two days²: Visit window +/- three days³: Visit window +/- five days⁴: Bilateral evaluation⁵: Injection to be performed after all other assessments have been performed.⁶: Results from Screening Visit B (V2) will be used for quantitative study analysis purposes.

Investigator may repeat any tests of Screening Visit B on a separate unscheduled visit if a difference in results is observed from Screening Visit A, as per investigator assessment

⁷: Study eye only

TABLE OF CONTENTS

INVESTIGATOR STATEMENT2

SUMMARY OF CHANGES3

SYNOPSIS4

LIST OF ABBREVIATIONS AND DEFINITION OF TERMS12

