3.5.1. Inclusion Criteria

Subjects meeting **ALL** of the following criteria will be considered eligible for clinical trial entry:

1. Subjects age 18 or older of any gender
2. Diagnosis of retinitis pigmentosa due to rhodopsin gene mutation, including P23H, confirmed previously by a CLIA or an investigational/academic lab
3. Impairment on VF in the opinion of the Investigator, as determined by perimetry
4. Willing to participate in the study as evidenced by signing of an informed consent document
5. Subjects of childbearing potential, both male and female, must agree to use two forms of birth control for the duration of the clinical trial. Males should continue to use the two forms of birth control for a minimum of three months after last injection. Females

of childbearing potential must use the two forms of birth control for a minimum of 30 days following their last injection

6. For females of child-bearing potential, subjects must have a negative pregnancy test at Screening and not lactating

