3.6. Strategies for Recruitment and Retention

Subjects will be recruited directly from the investigative sites' patient population or will be referred for treatment by other physicians. Once enrolled, subjects will be provided with the visit schedule and reminders from the clinical trial staff in advance of their visits to assist with compliance to the schedule of events for the clinical trial.

Subjects who discontinue early from investigational product treatment will complete the end-of-study visit (Week 16) at time of discontinuation. The Sponsor and Investigator will make all efforts to retain all subjects in the clinical trial until the end-of-study visit (Week 16) and to follow-up with early-discontinued subjects for safety purposes.

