7.8. Week 10 (Visit 8)—Cohort B only

- Perform Corneal Slit Lamp Safety Exam (Section 6.7.9)
- Collect samples for urine pregnancy test, if applicable (Section 6.6)
- Investigational Product Intravitreal Injection (Section 6.8)
- Prescribe artificial tears and/or lubricating ointment (Section 6.9)
- Collect concomitant medications (Section 6.4)
- Collect adverse events (Section 6.5)

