7.9. Week 12 (Visit 9)

- Perform BCVA (Section 6.7.1)
- Perform LLVA (Section 6.7.2)
- Perform Full Ophthalmic Examination (Section 6.7.7)
- Collect Wide Field Color and Autofluorescence Fundus Photographs (Section 6.7.8)
- Collect Macular Optical Coherence Tomography (Section 6.7.6)
- Collect Dark-Adapted Chromatic Perimetry (Section 6.7.5)
- Collect Macular Integrity Assessment (MAIA) (Section 6.7.3)
- Collect concomitant medications (Section 6.4)
- Collect adverse events (Section 6.5)
- Collect Full-field electroretinography (ERG) (Section 6.7.4)

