7.10. Week 16 (Visit 10)

- Perform BCVA (Section 6.7.1)
- Perform LLVA (Section 6.7.2)
- Perform Full Ophthalmic Examination (Section 6.7.7)
- Collect Wide Field Color and Autofluorescence Fundus Photographs (Section 6.7.8)
- Collect Macular Optical Coherence Tomography (Section 6.7.6)
- Collect Dark-Adapted Chromatic Perimetry (Section 6.7.5)
- Collect Macular Integrity Assessment (MAIA) (Section 6.7.3)
- Collect concomitant medications (Section 6.4)
- Collect adverse events (Section 6.5)

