8.7. Reporting Pregnancies

Pregnancies for women will be reported from the time the subject signs the informed consent form through final clinical trial visit or 30 days after the last IP administration, whichever is later. Males will report pregnancy of their partners through 90 days after the last IP administration.

Subjects who become pregnant will be withdrawn from the clinical trial. The pregnancy should be followed up to determine outcome, including spontaneous or voluntary termination, details of the birth, and the presence or absence of any birth defects, congenital abnormalities, or maternal and/or newborn complications.

Pregnancy should be recorded on a subject's source documents and a Pregnancy Notification and Outcome Form and reported using the same procedure for reporting SAEs detailed in Section 8.6.2. A pregnancy, by itself, is not an SAE. Pregnancy follow-up should also be recorded and should include an assessment of the possible relationship to the IP of any pregnancy outcome. Any pregnancy-related SAE (e.g., spontaneous abortion, birth defect) or any other SAE experienced during pregnancy must be recorded on a separate SAE Report Form and reported per SAE reporting procedures in Section 8.6.2.

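### Synopsis Inclusion Criterion 5 equates men's three months of contraception with 30 days after a visit label that contradicts itself; at the planned dates neither reading gives three months

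*Combined protocol and SAP*

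**What the plan says.** The synopsis version of Inclusion Criterion 5 requires men to go on using two contraceptive methods for "a minimum of three months after last injection (30 days after completion of Visit 9/Week 16"; the bracket closes at that point. The same criterion in Section 3.5.1 has no parenthesis: "Males should continue to use the two forms of birth control for a minimum of three months after last injection".

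The visit schedule is consistent elsewhere. Table 1 and Section 7.9 place Visit 9 at Week 12. Table 1 and Section 7.10 place the Week 16 assessment at Visit 10. Cohort A's third and last injection is at Week 8 (Visit 7) and Cohort B's sixth and last is at Week 10 (Visit 8), per Table 1 and Sections 7.7 and 7.8. Table 1 gives the visits from Week 6 to Week 16 a "Visit window +/- five days".

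On the related duty to report partner pregnancies, Section 8.7 counts in days from the last dose: "Males will report pregnancy of their partners through 90 days after the last IP administration".

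**The concern.** The parenthesis is the only part of the synopsis sentence that ties the three-month rule to a visit, so it is the part a site coordinator is most likely to turn into a stop date. It has two faults. It names a visit that does not exist, so the reader must choose between Week 12 and Week 16. And it fixes the end of the period by a visit, although the two cohorts have their last doses two weeks apart, so one visit-based date cannot stand for three months after last injection in both.

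What is at stake is reproductive-safety advice for an antifolate; Section 1.1 counts fetal cells among the tissues more sensitive to it. A man counselled from the parenthesis could stop contraception before the protocol's own minimum, and before the period in which Section 8.7 still wants partner pregnancies reported has ended.

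**Working it through.** **Inputs.** Section 7 sets Week 0 at Screening Visit B, where the first dose is given, so Week *n* is Day 7*n*.

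- Cohort A last injection, Week 8 (Table 1, Section 7.7): Day 56, in-window 51 to 61.
- Cohort B last injection, Week 10 (Table 1, Section 7.8): Day 70, in-window 65 to 75.
- Visit 9, Week 12 (Table 1, Section 7.9): Day 84, in-window 79 to 89.
- Visit 10, Week 16 (Table 1, Section 7.10): Day 112, in-window 107 to 117.
- Three months: 89 to 92 calendar days, depending on the start date; 90 days is used below, as in Section 8.7.

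**Formula.** Days of contraception after last dose = (day of the named visit + 30) − day of last injection. The shortest value pairs the earliest visit with the latest injection; the longest pairs the latest visit with the earliest injection.

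| Cohort and reading | Nominal | Shortest | Longest | Nominal shortfall from 90 |
|---|---|---|---|---|
| B, Week 16 | 112 + 30 − 70 = 72 | 107 + 30 − 75 = 62 | 117 + 30 − 65 = 82 | 18 |
| B, Visit 9 | 84 + 30 − 70 = 44 | 79 + 30 − 75 = 34 | 89 + 30 − 65 = 54 | 46 |
| A, Week 16 | 112 + 30 − 56 = 86 | 107 + 30 − 61 = 76 | 117 + 30 − 51 = 96 | 4 |
| A, Visit 9 | 84 + 30 − 56 = 58 | 79 + 30 − 61 = 48 | 89 + 30 − 51 = 68 | 32 |

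**Does the plan's own equivalence reproduce?** Not at the planned dates, in any of the four cases.

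**How often is it long enough?** Each visit has 11 in-window days, so there are 11 × 11 = 121 pairs of injection date and visit date.

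- Cohort B: the longest value is 82 days, which is 7 short of even the shortest three calendar months (89). None of the 121 pairs is long enough on either reading.
- Cohort A, Week 16 reading: reaching 90 requires Visit 10 to slip at least 4 days later relative to Visit 7. That is 7 + 6 + 5 + 4 + 3 + 2 + 1 = 28 of 121 pairs. At a threshold of 89 days it is 36 of 121.
- Cohort A, Visit 9 reading: the longest value is 68 days, so no pair is long enough.

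**What the rule implies.** Ninety days after a Week 10 dose is Day 70 + 90 = 160, which is 160 − 112 = 48 days after Week 16. For a Week 8 dose it is Day 56 + 90 = 146, or 34 days after Week 16.

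**The case against.** The strongest reply is that no rule is missing. The three-month minimum is stated in the same sentence, repeated without the parenthesis in Section 3.5.1, and matched by the 90 days of Section 8.7. Harm requires a site to prefer a bracketed remark naming a non-existent visit over the explicit minimum beside it. That stands, and it sets the severity. It does not make the parenthesis correct.

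It can also be said that the Cohort B result assumes the sixth dose is given. That stands too. A Cohort B man who missed the Week 10 dose but stayed to Week 16 would have his last dose at Week 8, and the Cohort A figures would apply: 86 days nominally, up to 96.

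Section 3.1 speaks of 16 weeks of follow-up after dosing, which might suggest that Week 16 counts from the last dose. Section 7 defines Week 0 otherwise, and Section 3.4 puts the ten visits within about 16 weeks. Even on that reading the parenthesis would give 112 + 30 = 142 days, again not three months.

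A reader might infer something stronger from Section 3.6, where a man who stops treatment early "will complete the end-of-study visit (Week 16) at time of discontinuation": that the parenthesis could then release him much sooner still. The documents do not support resting the point on that. Section 4.4 has every treated subject followed for safety over the scheduled course, Section 3.6 itself commits to retaining subjects and following those who stop early, and the first sentence of the criterion requires contraception for as long as the trial lasts.

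**Conclusion.** The parenthesis is wrong as written, and the fault is of low severity. Its visit label is self-contradictory. For a Cohort B man given the Week 10 dose it ends before three months on every in-window date, by 18 days nominally on the Week 16 reading and by 46 on the Visit 9 reading. For Cohort A it is 4 days short nominally on the Week 16 reading, although some in-window dates suffice, and 32 days short on the Visit 9 reading.

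These figures assume that visits and their windows count from Week 0 and that the planned last dose is given. The conclusion for Cohort B does not depend on whether three months is taken as 89, 90 or 92 days.

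A reader might infer that men in the trial will in fact be told to stop early. The documents do not show that: the consent form is not among the material reviewed, and the correct minimum is in the criterion itself. The finding is one of conflicting instructions in a safety criterion. No endpoint, analysis population or analysis is affected.

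**What to change.** Delete the parenthesis from synopsis Inclusion Criterion 5, so that its rule for men matches Section 3.5.1. Alternatively, replace it with: (90 days after last injection). That also agrees with Section 8.7. Either change ties the period to the last dose, so it works for both cohorts and for a man who misses a dose. If the consent form or any site counselling sheet carries the same parenthesis, correct it there too.

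The cost is one wording change. Visits, data collection and analysis stay as they are.

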ITT	Intent-to-Treat
ICH	International Council on Harmonisation
IND	Investigational New Drug Application
IP	Investigational Product
IOL	Intraocular lens
IOP	Intraocular pressure
IRB	Institutional Review Board
LLVA	Low Luminance Visual Acuity
MAIA/MAIAM	Macular Integrity Assessment (MAIA) Microperimetry
mL	Milliliters

mm	Millimeter
SD-OCT	Optical Coherence Tomography
QID	Four Times Daily
REB	Research Ethics Board
RP	Retinitis Pigmentosa
RR	Relative Risk
SAE	Serious Adverse Event/Serious Adverse Experience
US	United States
VA	Visual Acuity
WOCBP	Women of Childbearing Potential

1. INTRODUCTION

1.1. Background and Therapeutic Rationale

Retinitis pigmentosa (RP) is an inherited retinal disease that leads to a progressive degeneration of photoreceptors. Mutations within the rhodopsin gene account for approximately 25% of autosomal dominantly inherited RP cases. The mutation P23H (Substitution of Proline to Histidine at Codon 23 of the rhodopsin protein) is the most common mutation in the rhodopsin protein gene. The P23H mutation is associated with misfolded rhodopsin, which causes endoplasmic reticulum overload, activates the unfolded protein response and triggers apoptosis. Intravitreal methotrexate has been demonstrated in pre-clinical models of retinitis pigmentosa to promote clearance of misfolded rhodopsin without an adverse effect on wild type rhodopsin protein and improves electroretinogram (ERG) responses in P23H mutant rodents. (*Liu et al. (2020). Pharmacological clearance of misfolded rhodopsin for the treatment of RHO-associated retinitis pigmentosa. The FASEB Journal, 34(8), 10146–10167.*)

The clinical pharmacology of ADX-2191 (intravitreal methotrexate) is based on inhibition of dihydrofolic acid reductase. Dihydrofolates must be reduced to tetrahydrofolates before they can be utilized in the synthesis of purine nucleotides and thymidylate. Therefore, methotrexate interferes with deoxyribonucleic acid (DNA) synthesis, repair, and cellular replication. Actively proliferating tissues such as malignant cells, bone marrow, fetal cells, buccal, intestinal mucosa, and cells of the urinary bladder are in general more sensitive to this effect of methotrexate. When cellular proliferation in malignant tissues is greater than in most normal tissues, methotrexate may impair malignant growth without irreversible damage to normal tissues.

Intravitreal injection provides the clinician with a means to bypass the blood retinal barrier and provide more therapeutic doses of the methotrexate to the affected tissues than could otherwise be achieved through oral or systemic dosing.

Aldeyra is proposing to conduct an open-label Phase II clinical trial in subjects with retinitis pigmentosa due to rhodopsin mutations (including P23H) whom will be treated with serial intravitreal injections of ADX-2191 (methotrexate 0.8%) in the worse seeing eye.

